3.4.6. Adjustment for Multiple Hypothesis Testing

For the primary HRQOL analysis, adjustment for multiple comparisons of ELFI differences at specific times will be undertaken using the Hochberg method.(26) No formal adjustment will be used for other secondary or exploratory analyses. In general, two-sided P-values will be used and 95% confidence limits for all important endpoints will be reported.

3.5. Secondary Efficacy Analyses

3.5.1. Overall Survival

Overall survival between treatment groups will be analysed using a closed hierarchical method in the following pre-specified order: (1) palliative-intent treatment subgroup, (2) overall study population; and (3) adjuvant/curative-intent treatment subgroup.

Overall survival will be estimated using the non-parametric Kaplan-Meier method. Summary statistics will be presented with appropriate confidence intervals. The non-parametric log rank test will be used to compare the two arms of the study and, if appropriate, a Cox proportional hazard model will be used to estimate the treatment effects.

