
Page 8, INTEGERATE Synopsis:
 
 ➤ Added text: “stratified according to the following characteristics: treatment intent” 	Added variable for minimisation procedure for group allocation to reduce imbalance in variables that may influence primary endpoint	Minimise imbalance between treatment group of an additional variable that may influence primary endpoint

Page 9, INTEGERATE Synopsis:
 
 ➤ Changed text: “metastatic cancer receiving first line chemotherapy” 	Change in eligibility criteria	As above

Page 10, INTEGERATE Schematics of Study Design:
 
 ➤ Changed text: “Metastatic cancer in Adults ≥ 70 years with cancer, prior to commencing cytotoxic first line chemotherapy, targeted therapy, or immunotherapy” 	Change in eligibility criteria	As above

Page 13, Background:
 
 ➤ Changed text: “One randomised trial addressed short-term nurse-delivered geriatric intervention by advanced practice nurses” 	Update to literature review	None

➤ Added text: “A recent non-randomised prospective cohort study of 135 older adults with cancer looked at the impact of geriatrician-delivered CGA on chemotherapy toxicity and tolerance.(26) Participants in the intervention cohort underwent risk-stratification using a patient-completed screening questionnaire and high-risk patients received a geriatrician-delivered CGA. Participants in the intervention group were more likely to complete treatment as planned (odds ratio (OR) 4.14 (95% CI: 1.50-11.42), P=0.006) and fewer required treatment modification (OR 0.34 (95% CI: 0.16-0.73), P=0.006). Whilst there was a trend for fewer in the intervention group to develop grade 3+ toxicity, this did not reach statistical significance.”
		

Page 14, Background: ➤ Changed text: “Although Whilst the above studies one pilot study suggests a potential for CGA to improve outcomes interventions in medical oncology older adults with cancer, no randomised controlled trial testing the hypothesis that CGA can improve outcomes in this setting the chemotherapy setting has yet been published. In particular, no randomised controlled study has”
	Update to literature review	None

Page 15, Background: ➤ Changed text: “metastatic cancer receiving first line chemotherapy”
	Change in eligibility criteria	As above

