2.3. Treatment Allocation

2.3.1. Method of Treatment Allocation

Participants were randomly assigned via a computerised system using the method of minimisation (with a 80:20 random element) to receive integrated geriatric care or standard oncology care in a 1:1 ratio.(1) In this study, minimisation was used to achieve balance between groups using the following characteristics:

- treatment intent
- tumour type
- age
- gender
- ECOG performance status (physician-rated)

An 80:20 random element was determined to be the optimal value to reduce predictability whilst retaining balance.(2) This method was conducted using the MinimPy software package by a researcher not involved in the care of the study participants.(3)

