3.4.3. Primary HRQOL Analysis

The primary HRQOL analysis is defined prospectively as a comparison of the longitudinal change in ELFI scores for significant between-group difference using linear mixed models. The models will include baseline variables (baseline ELFI score, and possibly other baseline variables predictive of ELFI outcome) as covariates and treatment arm and time (and their interaction) as fixed effects. Time will include the baseline, 12 week, 18 week and 24 week assessment points. Time is continuous in linear mixed model.

These models account for covariance between repeated measures on participants and will be used to: i) describe the time course of the ELFI over time; ii) assess whether the time course differs between the two treatment arms by testing the study arm-by-time interaction; and iii) estimate and test differences between the two treatment arms at specific time points of interest via selected linear contrasts.

Linear mixed models account for missing data by using information from the observed data to implicitly impute unobserved data.

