3.4.3.1. Subgroup Analysis for the Primary Efficacy Endpoint

In addition to the analysis of the overall study population, subgroup analysis will be conducted for the ELFI (primary efficacy endpoint) using linear mixed models to detect significant differences in longitudinal change in ELFI score between treatment groups in the following subgroups: i) palliative-intent treatment subgroup; and ii) adjuvant/curative-intent treatment subgroup.

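### Allocation is minimised on five factors, but no analysis commits to them as a set: ELFI covariates are left open, the overall-population survival test states no strata, and the intent subgroups are tested without an interaction

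*Combined protocol and SAP*

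**What the plan says.** **Allocation.** SAP 2.3.1 (and protocol 3.4.1) assigns patients "using the method of minimisation (with a 80:20 random element) to receive integrated geriatric care or standard oncology care in a 1:1 ratio". The five factors are treatment intent, tumour type, age, gender and physician-rated ECOG status. The protocol's summary of change for Amendment 2 gives the reason for bringing in treatment intent: "Added variable for minimisation procedure for group allocation to reduce imbalance in variables that may influence primary endpoint".

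**Primary ELFI model.** SAP 3.4.3 states: "The models will include baseline variables (baseline ELFI score, and possibly other baseline variables predictive of ELFI outcome) as covariates". Arm, time and their interaction complete the model, and the only interaction tested is arm by time: "assess whether the time course differs between the two treatment arms by testing the study arm-by-time interaction".

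**Overall survival.** SAP 3.5.1 sets a closed order: palliative-intent subgroup, overall population, then adjuvant/curative-intent subgroup. On the test it says "The non-parametric log rank test will be used to compare the two arms of the study". A Cox model follows if appropriate. No strata or covariates are stated for either.

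**Subgroups.** SAP 3.4.3.1 analyses ELFI "using linear mixed models to detect significant differences in longitudinal change in ELFI score between treatment groups in the following subgroups", namely palliative intent and adjuvant/curative intent. SAP 3.5.3 repeats the two subgroups for the secondary endpoints. Neither section contains an arm-by-intent term.

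**General adjustment.** SAP 3.1 says confounding will be handled by logistic regression on age and other between-group differences, listing comorbidity, metastatic disease and dose reduction at the start of chemotherapy. It does not say which analyses this covers.

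**The concern.** Minimisation makes the arms more alike on the five factors than chance would. An analysis that leaves the factors out still counts the variation they explain as random error, so its standard error is too large. The test then rejects less than 5% of the time under the null and gives up power.

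Leaving the covariate set open also means that someone chooses covariates after seeing the data. The SAP is the final plan, so no later document closes that choice.

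The subgroup issue is different. Two significance tests in halves of a 128-patient trial will often disagree by chance. Without an interaction estimate, a split result can be read as benefit in one intent group only.

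**Working it through.** **Inputs from the documents:** effect size 0.5 SD, two-sided 0.05, 80% power, 64 evaluable per group (SAP 3.2.1); 1:1 minimisation with an 80:20 random element on five factors (SAP 2.3.1).

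**Assumed, because the documents give no figure:** the share R² of residual ELFI variance (after baseline ELFI) that the factors explain; the intent split; survival medians, hazard ratios and follow-up.

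**1. The plan's own figure.** n = 2(1.960 + 0.842)²/0.5² = 62.8, so 63 per arm by the normal approximation. The t-based calculation gives 63.77, so 64, with power 0.801. The stated 64 per group is reproduced.

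**2. ELFI with and without the factors.** This is a single-time-point approximation with exact balance. The standardised effect is 0.5 × √(64/2) = 2.828.

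- Size without the factors: 2[1 − Φ(1.960/√(1 − R²))]
- Power without: Φ((2.828 − 1.960)/√(1 − R²))
- Power with: Φ(2.828/√(1 − R²) − 1.960)

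| R² | Size without | Power without | Power with |
|---|---|---|---|
| 0.05 | 0.044 | 0.814 | 0.827 |
| 0.10 | 0.039 | 0.820 | 0.846 |
| 0.20 | 0.028 | 0.834 | 0.885 |

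Exact balance is the extreme case. A simulation of 80:20 minimisation (128 patients, 30,000 trials, assumed factor levels) gave sizes of 4.6%, 4.1% and 3.2% in the three rows: the same direction, somewhat closer to 5%.

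**3. Overall-population log-rank test.** Simulation: 5,000 trials per setting, 128 patients, 60% palliative, 12-month median in palliative controls, exponential survival, censoring uniform over 6 to 36 months, arms balanced within intent. Size is at treatment HR 1 and power at treatment HR 0.6.

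| Palliative vs curative HR | Size, unstratified | Size, stratified | Power, unstratified | Power, stratified |
|---|---|---|---|---|
| 2 | 0.047 | 0.053 | 0.496 | 0.520 |
| 4 | 0.028 | 0.048 | 0.389 | 0.464 |
| 6 | 0.025 | 0.053 | 0.332 | 0.445 |

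The differences in power are 2.4, 7.5 and 11.3 points. Monte Carlo error is about 0.7 points on each power, and a separate set of runs gave about 3 to 12 points, hence the range of about 2 to 12.

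**4. Separate subgroup tests when the true effect is 0.5 SD in both.** For a subgroup with n per arm, power p = Φ(0.5√(n/2) − 1.960). The chance that exactly one test is significant is p₁(1 − p₂) + p₂(1 − p₁).

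- Split 50:50, 32 and 32 per arm: p = 0.516 in each; 2 × 0.516 × 0.484 = 0.50.
- Split 60:40, 38.4 and 25.6 per arm: p = 0.591 and 0.432; chance 0.51.
- Split 70:30, 44.8 and 19.2 per arm: p = 0.658 and 0.341; 0.658 × 0.659 + 0.341 × 0.342 = 0.55.

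Under the null, two such tests at 0.05 give a 1 − 0.95² = 9.75% chance of at least one false positive. SAP 3.4.6 provides no adjustment outside the primary time-point contrasts.

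**5. Power of the interaction test for a 0.5 SD difference in effect.** Φ(0.5/√(2/n₁ + 2/n₂) − 1.960) is 0.29 at 50:50, 0.25 at 70:30 and 0.20 at 80:20.

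**The case against.** A reader might infer that the plan ignores the five factors, and treatment intent most of all. The text does not support that. Intent is the factor the plan uses most: it orders the survival tests and defines every subgroup. The primary model does not exclude the factors either; it permits further baseline variables without naming them. The defect is an uncommitted covariate set.

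SAP 3.1 can be offered as the missing adjustment. It names age, and metastatic disease is a rough proxy for intent. But logistic regression fits neither the ELFI mixed model nor survival, and only age among the five factors is named. Dose reduction at the outset may itself be affected by the intervention: protocol 3.7.1 counts initial-dose adjustments arising from the geriatric assessment as an outcome. The sentence does not answer the point.

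Other limits stand:

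- Survival tests (1) and (3) each lie within one intent level, so stratifying by intent matters only for test (2). That is a secondary endpoint, formally reached only if test (1) succeeds. It is also the gate to test (3), so power lost there carries forward.
- Baseline ELFI is already in the model and plausibly shares variance with ECOG status and age, so the further R² could be small. At 5% the gain is about one point of power.
- At an intent hazard ratio of 2, stratification gains only about 2 points.
- The interaction test is weak, so it cannot settle whether the effect differs by intent.

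**Conclusion.** The point holds in this form. The factors that governed allocation are not carried into the analysis by commitment, the overall-population survival analysis states no strata, and the intent subgroups are tested separately with no arm-by-intent term.

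It would be wrong to conclude that the ELFI or survival comparisons are biased or have inflated error. Leaving out balanced prognostic factors makes the ELFI and overall-population survival tests conservative, so a positive result would stand. The cost is power: roughly 1 to 5 points for ELFI at R² of 5% to 20%, and about 2 to 12 points for survival test (2). Both ranges rest on assumed inputs and near-exact balance.

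The most serious consequence is in the subgroups. A split verdict about half the time under an identical effect follows from the trial's own sample size and effect size plus an assumed intent split. This should be corrected, but it does not threaten the validity of the primary comparison.

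**What to change.** - **(a) SAP 3.4.3.** Replace the open-ended allowance for further covariates with the five minimisation factors as fixed covariates alongside baseline ELFI. State in advance how rare tumour types will be pooled.
- **(b) SAP 3.5.1.** Stratify the overall-population log-rank test and Cox model by treatment intent.
- **(c) SAP 3.4.3.1 and 3.5.3.** Replace the separate subgroup significance tests with one model per endpoint containing arm by intent (by time where the outcome is longitudinal). Report the interaction estimate and the subgroup effects, each with a confidence interval. State that the interaction test has only about 20% to 29% power for a 0.5 SD difference in effect, so a non-significant result does not show that the effect is the same in both groups.
- **(d) SAP 3.1.** Delete the logistic-regression sentence, or limit it to binary endpoints with a named covariate list.

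The cost is SAP wording and a few degrees of freedom. No new data are needed, since all five factors were recorded for allocation.

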3.5.2. Other Secondary Endpoints

Other secondary endpoints will be summarised according to established guidelines specific to the measurement instrument. In general, categorical variables will be tabulated and key summary statistics (mean, standard deviation, median, range, etc.) will be presented for continuous measurements. Comparisons between treatment arms will be made where appropriate and the test selected depending on the distribution.

Secondary endpoints were specified in the protocol as follows:

- Performance Status The mean self-rated ECOG score and KPS score of patients at 12 weeks and 24 weeks are secondary endpoints; they will be compared between treatment arms.
- Functional Status The proportion of participants in each treatment arm with functional decline in the ADL and/or IADL scores at 12 weeks and 24 weeks are secondary endpoints of this study; they will be compared between treatment arms.
- Mood The proportion of participants in each of the PHQ-9 and GAD-7 categories (cut-points 5, 10 and 15) in the two treatment arms at 12 weeks and 24 weeks are secondary endpoints of this study; they will be compared between treatment arms.
- Nutrition The proportion of participants with self-MNA score ≤ 11 points and >11 points in the two treatment arms at 12 weeks and 24 weeks is a secondary endpoint of this study and will be compared between treatment arms.
- Health Utility The EQ-5D-5L health utility score in the two treatment arms at 12 weeks and 24 weeks are secondary endpoints of this study and will be compared between treatment arms.
- Chemotherapy delivery Secondary endpoints of this study are the mean RDI of chemotherapy, the proportion of participants with dose reduction $\geq 10\%$ from previous dose; they will be compared between treatment arms.
- Healthcare utilisation Secondary endpoints of this study are the mean number of: emergency department visits, hospital admissions (including length of hospital stay; and divided into planned and unplanned), medical consultations and type of PBS-listed medications in the two treatment arms from randomisation to 12 weeks and 24 weeks post-randomisation; they will be compared between treatment arms. An additional secondary endpoint is the hazard ratio for hospitalisation of participants in the two treatment arms; this will be compared between treatment arms.
- Institutionalisation A secondary endpoint of this study is the hazard ratio of institutionalisation of participants in the two treatment arms; this will be compared between treatment arms. In addition, the level of care level of care and social situation will also be described in the treatment arms.

The following endpoint definition was changed from the protocol:

- Chemotherapy delivery: the proportion of participants with dose delays in the two treatment arms at 12 weeks and 24 weeks. Dose delay is defined as a delay of more than 3 days in the start of chemotherapy measured since the start of the previous cycle.

The following endpoints were not defined in the protocol, but will be analysed as exploratory endpoints to supplement the pre-specified secondary endpoints:

- QLU-C10D health utility
- QLU-C10D health utility score in the two treatment arms at 12 weeks and 24 weeks will be compared between treatment arms.(27, 28)
- The QLU-C10D health utility scores will also be used in the health economic analysis, in place of the EQ-5D-5L scores, to determine if the same or different conclusions would be reached with either utility measure.
- Chemotherapy delivery
- Primary dose reduction (PDR) will be compared within treatment arms. PDR is defined as dose of chemotherapy which is less than the dose recommended for given regimen in current treatment guidelines by NCCN (excluding round-off).
- Mean % dose reduction at outset will be compared within treatment arms.
- Median % dose reduction at outset will be compared within treatment arms.
- Early discontinuation of chemotherapy will be compared within treatment arms.
- Mean cycles of chemotherapy delivered will be compared within treatment arms.
- Median cycles of chemotherapy delivered will be compared within treatment arms.

Table 4. Summary of secondary and additional exploratory endpoints, data type, data timepoints and statistical tests are listed in the table below.

Endpoints	Data Type	Data output	Data Timepoints	Statistical Tests
Function				
ECOG-PS	Categorical ordinal (0,1,2,3,4)	contingency table	Baseline Wk12 Wk24	contingency table analysis
KPS	Categorical ordinal (30,40,50,60,70,80,90,100)	contingency table	Baseline Wk12 Wk24	contingency table analysis
Katz ADL scale	6-item, categorical dichotomous scale (i) → dichotomous outcome (unimpaired, impaired) (ii) → dichotomous outcome (any decrease in ADL)	1. unimpaired vs impaired 2. decrease in ADL	Baseline Wk12 Wk24	contingency table analysis
OARS IADL	7-item, 3-point Likert scale (i) → categorical dichotomous (unimpaired, impaired) (ii) → categorical dichotomous (any decrease in IADL)	1. unimpaired vs impaired 2. decrease in IADL	Baseline Wk12 Wk24	contingency table analysis
Mood				
PHQ9 (depression)	9-item, 4-point Likert scale → categorical ordinal (none, mild, moderate, severe) → categorical dichotomous (not depressed, depressed)	contingency table	Baseline Wk12 Wk24	contingency table analysis
GAD7 (anxiety)	9-item, 4-point Likert scale → categorical ordinal (none, mild, moderate, severe) → categorical dichotomous (not anxious, anxious)	contingency table	Baseline Wk12 Wk24	contingency table analysis
Nutrition				
Self-MNA	6-item questionnaire → categorical dichotomous (malnourished/at risk vs normal) → categorical ordinal (malnourished, at-risk, normal)	1. malnourished/at risk vs normal 2. malnourished vs at-risk vs normal 3. decrease in self-MNA	Baseline Wk12 Wk24	contingency table analysis
Health Utilities				
EQ-5D-5L	5-item, 5-point Likert scale, weighted with Australian utility weights	mean utility weight	Baseline Wk12 Wk18 Wk24	t-test (parametric); or Mann-Whitney test (non-parametric)
QLU-C10D	10-dimensions derived from 13 items of the QLQ-C30, each dimension weighted with Australian utility weights	mean utility weight	Baseline Wk12 Wk18 Wk24	t-test (parametric); or Mann-Whitney test (non-parametric)
Chemotherapy Delivery				
Initial dose (i.e. primary dose reduction)	Categorical dichotomous (full dose, reduced dose)	full dose vs reduced dose	Baseline	contingency table analysis
Mean % dose reduction at outset where applicable	Numerical	mean	Baseline	t-test (parametric); or Mann-Whitney test (non-parametric)
Median % dose reduction at outset where applicable	Numerical	median	Baseline	Mann-Whitney test (non-parametric)
Subsequent dose reduction ≥10%	Categorical dichotomous (yes, no)	yes vs no		contingency table analysis
Subsequent dose escalation	Categorical dichotomous (yes, no)	yes vs no		contingency table analysis
Dose delay >3 days	Categorical dichotomous (yes, no)	yes vs no		contingency table analysis

Early discontinuation	Categorical dichotomous (yes, no)	yes vs no		contingency table analysis
Mean Relative Dose Intensity (RDI)	Numerical	mean		t-test (parametric); or Mann-Whitney test (non-parametric)
Mean cycles delivered	Numerical	mean		t-test (parametric); or Mann-Whitney test (non-parametric)
Median cycles delivered	Numerical	Median		Mann-Whitney test (non-parametric)
Healthcare Utilisation				
Mean number of emergency department visits	Numerical	mean	Baseline Wk12 Wk18 Wk24	t-test (parametric); or Mann-Whitney test (non-parametric)
Mean number of hospital admissions (total)	Numerical	mean	Baseline Wk12 Wk18 Wk24	t-test (parametric); or Mann-Whitney test (non-parametric)
Mean number of hospital admissions (unplanned)	Numerical	mean	Baseline Wk12 Wk18 Wk24	t-test (parametric); or Mann-Whitney test (non-parametric)
Mean number of hospital admissions (planned)	Numerical	mean	Baseline Wk12 Wk18 Wk24	t-test (parametric); or Mann-Whitney test (non-parametric)
Mean number of hospital admissions (inpatient palliative care)	Numerical	mean	Baseline Wk12 Wk18 Wk24	t-test (parametric); or Mann-Whitney test (non-parametric)
Mean number of medical consultations	Numerical	mean	Baseline Wk12 Wk18 Wk24	t-test (parametric); or Mann-Whitney test (non-parametric)
Mean number of medications	Numerical	mean	Baseline Wk12 Wk18 Wk24	t-test (parametric); or Mann-Whitney test (non-parametric)
Involvement of allied health (physiotherapist, occupational therapist, dietitian, social worker)	Categorical dichotomous (yes, no)	1. mean 2. time to referral 3. time to review	Baseline Wk12 Wk18 Wk24 Longitudinal	1. t-test (parametric); or Mann-Whitney test (non-parametric) 2. time-to-event analysis
Referrals to oncology rehabilitation program	Categorical dichotomous (yes, no)	1. mean 2. time to referral	Baseline Wk12 Wk18 Wk24 Longitudinal	1. t-test (parametric); or Mann-Whitney test (non-parametric) 2. time-to-event analysis
Participation in oncology rehabilitation program	Categorical dichotomous (yes, no)	1. mean 2. time to participation	Baseline Wk12	1. t-test (parametric); or

			Wk18 Wk24 Longitudinal	Mann-Whitney test (non-parametric) 2. time-to-event analysis
Referrals to MyAgedCare	Categorical dichotomous (yes, no)	1. mean 2. time to referral	Baseline Wk12 Wk18 Wk24 Longitudinal	1. t-test (parametric); or Mann-Whitney test (non-parametric) 2. time-to-event analysis
Seen by Aged Care Assessment Service	Categorical dichotomous (yes, no)	1. mean 2. time to review	Baseline Wk12 Wk18 Wk24 Longitudinal	1. t-test (parametric); or Mann-Whitney test (non-parametric) 2. time-to-event analysis
Referrals to Community Palliative Care	Categorical dichotomous (yes, no)	1. mean 2. time to referral	Baseline Wk12 Wk18 Wk24 Longitudinal	1. t-test (parametric); or Mann-Whitney test (non-parametric) 2. time-to-event analysis
Seen by Community Palliative Care	Categorical dichotomous (yes, no)	1. mean 2. time to review	Baseline Wk12 Wk18 Wk24 Longitudinal	1. t-test (parametric); or Mann-Whitney test (non-parametric) 2. time-to-event analysis
Institutionalisation				
Institutionalisation (residential care or supported residential services)	Categorical dichotomous (yes, no)	1. yes vs no 2. time to institutionalisation	Baseline Wk12 Wk24 Longitudinal	1. Contingency table analysis 2. time-to-event analysis
Social situation	→ Categorical ordinal (fully independent, low, high) → Categorical dichotomous (fully independent, assisted)	1. yes vs no 2. time to dependence	Baseline Wk12 Wk24 Longitudinal	1. Contingency table analysis 2. time-to-event analysis

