2.7.2.3. Activities of Daily Living (ADL) and Instrumental Activities of Daily Living (IADL)

In geriatric medicine, ADL and IADL is used to assess functional status and is part of routine geriatric assessment.(8) Decline in functional status is associated with adverse health outcomes such as mortality and residential care placement for older hospitalised patients. Self-reported Katz ADL scale and OARS IADL scale will be used to describe the functioning level in of the study population.(9, 10)

Katz ADL scale assesses adequacy of performance in basic activities of daily living: bathing, dressing, toileting, transferring, continence, and feeding. Each item are scored yes/no for independence in each of the six functions. A summary score ranges from 0 (unable to perform any activity) to 6 (able to perform all activities).

OARS IADL is an easy to administer assessment instrument that provides self-reported information about functional skills necessary for independent living in the community. These skills are considered more complex than the basic activities of daily living as measured by the Katz ADL scale. The 7-items on the OARS IADL assesses the following domains of function: telephone, shopping, food preparation, housekeeping, mode of transportation, medications and finances. Each item is scored on a 3-point Likert-like scale, with the total score ranging from 0 (unable to perform any activity) to 14 (able to perform all activities).

Disability in ADL and IADL is defined as the need for assistance to complete at least one ADL or IADL, respectively. Functional decline in ADL and IADL is defined as any decrease in ADL and/or IADL score between baseline and follow-up assessments.

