2.7.2.4. Mood

Anxiety and depression are common symptoms in patients with advanced cancer. Integrated geriatric care may alleviate some of these symptoms by providing additional support and reducing social isolation.

PHQ-9 and GAD-7 will be used to measure the prevalence of depression and anxiety in the study population. PHQ-9 and GAD-7 are subscales of the Patient Health Questionnaire, a patient self-rated version of the Primary Care Evaluation of Mental Disorders which is a widely used screening tool for mental health disorders in primary care.(11)

The PHQ-9 is a brief, self-rated questionnaire that was developed to screen for depression. It has 9-items derived from the Diagnostic and Statistical Manual of Mental Disorders, 4th Edition, Text Revision (DSM-IV-TR) criteria for major depressive disorder.(12) For each item the participant is asked to rate how much over the 2 weeks they have been bothered by the symptoms. Scoring is on a Likert-type scale from 0 to 3 (0 indicates not at all; 1 indicates several days; 2 indicates more than half the days; 3 indicates nearly every day). The PHQ-9 scored as a continuous measure has good discriminating power between cases and non-cases of major depressive disorder in cancer outpatients, with an area under the curve (AUC) of 0.94 (95% confidence interval [CI], 0.93-0.95) on ROC analysis.(13)

The GAD-7 is a brief, self-rated questionnaire which was originally developed as a screen for Generalised Anxiety Disorder (GAD), and is frequently used in conjunction with the PHQ-9.(14) Scoring of its 7-item is on a Likert-type scale from 0 to 3 (0 indicates not at all; 1 indicates several days; 2 indicates more than half the days; 3 indicates nearly every day). Anxiety in cancer is thought to be most closely related to the free floating anxiety characteristic of GAD.(15). The GAD-7 is gaining use in screening for a range of anxiety disorders due to its brevity and good psychometric properties.

An estimate of clinically important levels of depression and anxiety can be made using cut-off scores for PHQ-9 and GAD-7. Scores of 5, 10, 15 represent cutpoints for mild, moderate, and severe levels of depression and anxiety, on the PHQ-9 and GAD-7 respectively.(14) A recommended cutpoint for further evaluation and treatment is a score of 10 or more on both measures.(14) A score of 9 or less requires no action or monitoring.

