3.2. Sample size

3.2.1. Sample size required

Based on reviews of published studies, a minimal important difference in patient-reported outcome scores has commonly been set at approximately half the standard deviation; that is, equivalent to an effect size of 0.50.(20, 21) An effect size of 0.5 is commonly regarded as a medium difference and a meta-analysis has shown it to be clinically relevant in studies of quality of life using QLQ-C30 as an outcome measure.(22, 23)

The target sample for this study was based on an independent t-test at a 2-sided significance level of 0.05 to have an 80% power to detect a significant between-group difference in ELFI from baseline to 12 weeks with an effect size of 0.5. Under these assumptions, the minimum sample size is 64 evaluable participants in each group (or a total of approximately 128 evaluable participants) who have completed the primary outcome measure at two separate timepoints.

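### Mood, nutrition and daily-function scores are tested only after being cut into categories; a baseline-adjusted comparison of the full scores should be added beside the protocol-defined proportions

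*Combined protocol and SAP*

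**What the plan says.** For mood, SAP 3.5.2 compares "The proportion of participants in each of the PHQ-9 and GAD-7 categories (cut-points 5, 10 and 15) in the two treatment arms" at weeks 12 and 24. Table 4 adds a depressed/not depressed and an anxious/not anxious split without stating the cut there.

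For nutrition, the endpoint is self-MNA at 11 or below against above 11. Table 4 lists this as "categorical dichotomous (malnourished/at risk vs normal" and adds a three-band version and a decrease in self-MNA.

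For daily function, SAP 2.7.2.3 states: "Functional decline in ADL and IADL is defined as any decrease in ADL and/or IADL score between baseline and follow-up assessments". Table 4 also lists unimpaired against impaired for both ADL and IADL.

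Contingency table analysis is the only test that Table 4 gives for these five instruments, and it does not say which one. SAP 3.1 allows either chi-square or Fisher's exact test for categorical data. Fisher alone is named only in SAP 3.4.4, for ELFI deterioration.

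The underlying scores are numeric: self-MNA 0 to 14, Katz ADL 0 to 6, OARS IADL 0 to 14, and PHQ-9 and GAD-7 items each scored 0 to 3 (SAP 2.7.2.3 to 2.7.2.5). The schedule in SAP 2.5.1 collects them in both arms at baseline, week 12 and week 24. In the same Table 4, EQ-5D-5L and QLU-C10D are tested as scores, by t-test or Mann-Whitney.

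**The concern.** Function, mood and nutrition are named secondary objectives, and SAP 1.3 hypothesises improvement in each. Cutting a numeric score discards the differences within each category. Any decrease gives a one-point loss the same weight as a large one, and does not separate improvement from no change. The loss of information makes a real effect more likely to be reported as no difference. The plan gives no reason for treating these five scales differently from the two utility scores in the same table. SAP 3.5.2 does promise means and standard deviations for continuous measurements, but as summaries; Table 4 is where tests are assigned, and it assigns none to these total scores.

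**Working it through.** **Inputs.** Two-sided 5%, 80% power, effect size 0.5 and 64 evaluable per arm, all from SAP 3.2.1, where they apply to ELFI at 12 weeks: "independent t-test at a 2-sided significance level of 0.05 to have an 80% power" and "the minimum sample size is 64 evaluable participants in each group (or a total of approximately 128 evaluable participants". Allocation is 1:1 (SAP 2.3.1). SAP 3.4.6 adjusts no secondary test for multiplicity, so each is at 5%. The documents give no target effect and no expected category rates for these secondary endpoints. The 0.5 SD effect is therefore carried over from ELFI as an assumption, and the control-arm rate is varied.

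**Step 1: the plan's own figure.** For a two-sample t-test, the noncentrality is 0.5 × √(64/2) = 2.83 on 126 degrees of freedom, which gives power 80.1%. At 63 per arm it is 79.5%. The stated 64 per arm is reproduced. Mann-Whitney on the same normal score gives about 79%.

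**Step 2: a yes/no cut of the same score.** If a proportion p of controls falls in the adverse category and the score shifts by 0.5 SD, the intervention proportion is Φ(Φ⁻¹(p) − 0.5). Chi-square power is Φ[(d − 1.96·se₀)/se₁], where d is the difference in proportions, se₀ uses the pooled proportion and se₁ the separate ones. Example with p = 30%: Φ(−0.524 − 0.5) = 15.3%; d = 0.147; se₀ = √(2 × 0.2265 × 0.7735/64) = 0.0740; se₁ = √((0.300 × 0.700 + 0.153 × 0.847)/64) = 0.0728; power about 51%. Fisher power is by exact enumeration.

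| Control rate | Intervention rate | Chi-square power | Fisher power | n per arm for 80% (chi-square) |
|---|---|---|---|---|
| 10% | 3.7% | 29% | 16% | 256 |
| 20% | 9.0% | 42% | 34% | 160 |
| 30% | 15.3% | 51% | 44% | 126 |
| 40% | 22.6% | 57% | 49% | 110 |
| 50% | 30.9% | 60% | 55% | 102 |
| 60% | 40.3% | 61% | 53% | 100 |
| 70% | 51.0% | 60% | 54% | 103 |
| 80% | 63.4% | 55% | 48% | 115 |
| 90% | 78.3% | 44% | 36% | 152 |

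Chi-square power is 50% or less when the control rate is below about 28% or above about 86%. Fisher is below 50% in the table at 40% and under, and at 80% and over.

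**Step 3: ordered bands.** These were simulated with the same latent shift, 64 per arm and 20,000 runs. For four bands, with control splits ranging from equal quarters to 70/20/7/3, Pearson chi-square has 35–56% power and an ordinal (rank or trend) test 53–73%. For three bands, Pearson has 45–59% and an ordinal test 56–69%.

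**Step 4: the full score adjusted for baseline.** The residual SD is multiplied by √(1 − r²). Assumed baseline/follow-up correlations of 0.3, 0.5 and 0.7 give power of 84%, 90% and 98% (normal approximation).

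**Step 5: limits.** The normal model fits Katz ADL poorly, because its range is 0 to 6 and many participants may sit at the top. With an assumed 69–84% at ceiling at baseline, simulated power is 42–51% for any decrease, 49–62% for Mann-Whitney on the change and 57–72% for a baseline-adjusted score. The like-for-like gain is thus about 7 to 11 points (49 − 42 and 62 − 51). These figures depend on assumed distributions and are indicative only. If fewer than 64 per arm remain at week 24, both approaches lose power: at an assumed 51 per arm, 71% on the full score and at most about 51% on a yes/no cut.

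**The case against.** These are protocol-defined endpoints (Protocol 3.7.3.3 to 3.7.3.5), none of them is powered, and the cuts have clinical meaning. SAP 2.7.2.4 ties the mood cut-points to clinically important levels, and SAP 2.7.2.5 links the self-MNA cut to a predictor of early death. Table 4 is also broader than any decrease alone: unimpaired against impaired can register recovery. Physical and role function are tested on a full scale through ELFI, and emotional functioning through the QLQ-C30 tertiary analyses (SAP 3.4.5). The trial is open-label and the SAP describes allocation in the past tense, so replacing or demoting these endpoints now would be a late endpoint change. All of this stands. It rules out demotion of the proportions, but not a supplementary score analysis.

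A reader might infer that a 0.5 SD effect would be missed half the time or more throughout. The documents do not support that: the test is unnamed, central cuts by chi-square miss about 39–43%, and an ordinal test on four bands misses 27–47%. Nor is a single PHQ-9 cut at 10 a fair picture of the mood endpoint, which is four bands.

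A reader might also take "The PHQ-9 scored as a continuous measure has good discriminating power between cases and non-cases of major depressive disorder in cancer outpatients" as the SAP endorsing a continuous outcome analysis. That sentence concerns diagnostic discrimination and does not settle how to compare arms.

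**Conclusion.** The point holds as an inexpensive improvement to the secondary analyses. Under a 0.5 SD effect, 64 per arm and a roughly normal score, cutting lowers power from 80% to at most about 61% (chi-square) or 55% (Fisher). The effect is missed about 40% of the time at best. It is missed half the time or more when the control rate is below about 28%, and for many cuts if Fisher is used. Four bands give about 35–56% by Pearson and 53–73% by an ordinal test. The gain is smaller for Katz ADL because of its ceiling. These sizes rest on an effect borrowed from ELFI and on assumed control rates. The primary conclusion is unaffected.

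**What to change.** Keep the protocol-defined proportions as the secondary endpoints. Before analysis begins, amend SAP 3.5.2 and Table 4 as follows.

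- Add a supplementary between-arm comparison of the total score for PHQ-9, GAD-7, self-MNA, Katz ADL and OARS IADL at weeks 12 and 24, with a 95% confidence interval and adjustment for the baseline score. Use a rank-based or ordinal model where the ceiling is heavy, as for ADL.
- List these comparisons among the exploratory endpoints that SAP 3.5.2 identifies as not defined in the protocol.
- For the ordered PHQ-9, GAD-7 and self-MNA bands, name an ordinal (trend or rank) test in place of the general contingency-table entry.

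The cost is SAP wording and 5 × 2 = 10 further unadjusted comparisons on data already collected. Table 4 already implies 22 for these scales: 11 categorised versions (ADL 2, IADL 2, PHQ-9 2, GAD-7 2, self-MNA 3) at two follow-up times. A score difference is also less directly clinical than a proportion, which is why the proportions stay beside it.
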